1.2 Background and Rationale

1.2.1 Overview of the Disease State

SLE is a chronic inflammatory autoimmune disease that has variable manifestations in multiple organ systems and follows a relapsing and remitting course. The disease process includes abnormal immune responses mediated by tissue-binding autoantibodies and immune complex deposition, giving rise to tissue damage often resulting in end organ disease and even mortality. Survival of SLE has improved due to earlier detection, improved overall medical care, and standardized SLE treatment with corticosteroids, immunosuppressants, and cytotoxic agents.¹ However, some of the morbidity in patients with SLE is related to its treatment. Comparison of early and late outcomes in patients with SLE demonstrate that death in early disease is most commonly due to infections and active SLE causing multi-system organ damage, while thromboses were the most common cause of death during later disease.²

The reported prevalence of SLE in the United States (US) is 20 to 70 cases per 100,000 people.³ More than 90% of cases of SLE occur in women, frequently starting at childbearing age. Women of color are disproportionately affected by SLE. This suggests multiple genetic and environmental factors are at play. Accordingly, a multifactorial view of the immunopathogenesis of SLE suggests more than 1 area of interest, including breach in central tolerance in the adaptive arm of the immune system, peripheral amplification of the autoimmune response by the innate immune system, and local processes in the target organ that facilitate end-organ disease.⁴

1.2.2 BOS161721 Development

Boston Pharmaceuticals is developing BOS161721 for the treatment of SLE. BOS161721 is a humanized immunoglobulin G1 (IgG1) mAb directed against human IL-21.

Murine mAb 19E3, the progenitor of BOS161721, was generated using mouse hybridoma technology. 19E3 has subpicomolar (pM) affinity to human IL-21 and was selected for its potent neutralization of IL-21 bioactivity. BOS161721 was generated by the humanization of mAb 19E3 where its complementarity-determining regions were grafted onto a human IgG1 kappa backbone. The fragment crystallizable (Fc) portion of BOS161721 contains a YTE (M252Y/S254T/T256E triple mutation) in the constant domain of the IgG1 heavy chain that was introduced into the parental molecule, 19E3, intended to prolong the in vivo terminal elimination half-life ($t_{1/2}$) of the mAb.⁵ Thus, BOS161721 retains sub-pM binding to IL-21 and prevents IL-21 from binding to the IL-21 receptor (IL-21R), inhibiting IL-21 bioactivity.

BOS161721 binds to human IL-21 and Cynomolgus monkey IL-21, which are highly homologous, and neutralizes the bioactivity of both. BOS161721 is specific for IL-21 as it does not bind to or inhibit the other gamma-chain (γ c) family of cytokines, and acts to specifically neutralize the IL-21 pathway. In *in vitro* studies, BOS161721 inhibited downstream IL-21-induced signaling, IL-21-induced plasma cell differentiation, and IL-21-induced natural killer (NK) cell activation. In *in vivo* studies, BOS161721 significantly inhibited the T-cell dependent antibody response (TDAR) to immunization with a protein antigen as well as B-cell expansion following a second protein antigen immunization in Cynomolgus monkeys.

1.2.2.1 Interleukin-21

IL-21 is an inflammatory cytokine, which belongs to a family of cytokines that also includes IL-2, IL-4, IL-7, IL-9, and IL-15, all of which bind to private receptors in complex with the common cytokine receptor γ c.⁶ Most cytokines in this family are critically important for both the maintenance and function of T-cell and B-cell responses. IL-21 signals through a receptor complex consisting of its own private receptor, the IL-21R and γ c.^{6,7} Engagement of the IL-21R/ γ c complex leads to the activation of several signaling pathways, including the Janus kinase/signal transducer and activator of transcription, mitogen-activated protein kinase (MAPK) and phosphoinositide 3-kinase pathways.⁸ IL-21 is produced mainly by T-cells and NK T-cells, but neutrophils have also been reported to produce IL-21.^{9,10} The IL-21R is expressed on a broad array of cell types, including B-cells, T-cells, NK-cells, macrophages and dendritic cells, as well as other hematopoietic and nonhematopoietic cells such as fibroblasts, keratinocytes, and intestinal epithelial cells.^{9,11} Activation of signal transducer and activator of transcription 3 (STAT3) via phosphorylation is critical in regulating human B-cell responses to IL-21¹²; phosphorylated STAT3 (pSTAT3) forms a homodimer, which translocates to the nucleus where it initiates transcription of the IL-21 gene, forming an autocrine loop for IL-21 production via STAT3 phosphorylation.¹³ In addition, IL-21 has been shown to upregulate expression of its own receptor¹⁴ and induces an autocrine feedback loop.¹⁵

IL-21 modulates various aspects of immune function. It promotes cluster of differentiation 4 (CD4+) T-cell differentiation and promotes the generation of T-helper (Th)17¹⁶ and T-follicular helper (Tfh) cells.^{15,17} In mice, IL-21 has been shown to regulate the balance between Th17 and regulatory T-cell (Treg), in that it increases Th17, while inhibiting Treg differentiation.¹⁸ Less is understood with regards to human Tregs, although IL-21 has been reported to counteract Treg suppression of human effector T-cells¹⁹ and blockade of IL-21 promotes Treg generation in a murine model of graft versus host disease induced by human T-cells.²⁰ IL-21 upregulates CD8+ T-cell and NK-cell expansion and cytolytic activity by increasing granzyme B and perforin.^{21,22} IL-21 also has been reported to increase granzyme B in plasmacytoid dendritic cells and B-cells resulting in inhibition of T-cell responses.^{23,24} IL-21 also has a variety of effects on nonhematopoietic cells, such as stromal cells and induces inflammation through matrix metalloproteinase release by gut intestinal fibroblasts.²⁵

One principal non-redundant role of IL-21 is the promotion of B-cell activation, differentiation, or death during humoral immune responses.¹⁴ Furthermore, increased IL-21 production is characteristic of several autoimmune diseases and is likely to contribute to autoantibody production as well as pathologic features of autoimmune disease.²⁶ The critical role of IL-21 in promoting humoral and other immune responses makes it an important focus of potential

therapeutic interventions in conditions characterized by overproduction of pathogenic autoantibodies. IL-21 production by Tfh cells in humans is believed to play a major role in driving the autoantibody production through its role in plasma cell differentiation. Importantly, Tfh cell populations are expanded in patients with autoimmune diseases such as lupus, bullous pemphigoid, rheumatoid arthritis (RA) and primary Sjögren's syndrome (pSS) and have been reported to correlate with IL-21 levels, autoantibodies, and disease severity.^{26,27,28,29} Furthermore, loss of number and functionality of Tregs has been associated with autoimmune diseases such as SLE and giant cell arteritis, which IL-21 is expected to modulate.^{30,31} Thus, neutralization of IL-21 in settings of autoimmunity is expected to impact several cell populations believed to be involved in the pathogenesis of autoimmune disorders including SLE.

BOS161721 selectively binds IL-21 with high affinity to neutralize IL-21, and due to its pleiotropic nature, neutralization of IL-21 is expected to impact several cell populations believed to be involved in the pathogenesis of SLE. Importantly, patients with SLE have elevated IL-21 plasma levels that correlate with the severity of the disease. Recently, genome-wide association studies (GWAS) have provided convincing evidence that the chromosomal 4q 27 region harbors the IL-21 genes and is associated with chronic inflammatory disorders, including SLE.²⁹

1.2.2.2 Preclinical Studies

The pharmacokinetics (PK) of BOS161721 were characterized following single-dose intravenous (IV) administration of BOS161721 (0.01 to 30 mg/kg) in male Cynomolgus monkeys or repeat, every 2 weeks IV administration (15 to 100 mg/kg) and subcutaneous (SC) administration (50 mg/kg) in male and female Cynomolgus monkeys. Systemic exposure was approximately dose-proportional within the tested dose range. SC bioavailability was determined to be 64.3%.

CCI

Two single-dose (IV) non-good laboratory practice (GLP) studies conducted in Cynomolgus monkeys evaluated the toxicity, pharmacodynamics (PD), toxicokinetics (TK), and immunogenicity of BOS161721. Following a single IV administration (slow bolus), there were no BOS161721-related adverse changes, resulting in a no-observed-adverse-effect-level (NOAEL) value of 30 mg/kg, the highest dose tested among 2 studies. CCI

In a repeat-dose GLP toxicology study in Cynomolgus monkeys, BOS161721 was administered every 2 weeks by IV or SC (50 mg/kg) administration for 3 months (a total of 7 doses). CCI

CCI

The NOAELs were determined to be 100 mg/kg IV and 50 mg/kg SC, the highest doses tested.

1.2.2.3 Clinical Studies

BOS161721-01 was a double-blind, Phase 1, single ascending dose (SAD) study to assess the safety, PK, and PD of BOS161721 in healthy subjects. The primary objective of the study was to characterize the safety and tolerability of IV and SC SADs of BOS161721 in an otherwise healthy subject population without concomitant illnesses, immune abnormalities, or concomitant medications. Secondary objectives included characterization of the PK and immunogenicity of BOS161721, and exploratory objectives included the evaluation of the effect of BOS161721 on TDAR to keyhole limpet hemocyanin (KLH) (primary and secondary immunizations) in healthy subjects, the effects of BOS161721 on plasma levels of IL-21 (free and bound), and the evaluation of the effect of BOS161721 on IL-21 gene expression (via gene signature) in blood. This study consisted of 8 cohorts. Subjects were randomized in a 3:1 ratio (BOS161721: placebo) and received either a single dose of BOS161721 (1 [IV], 3 [SC], 10 [SC], 22 [IV], 30 [SC], 60 [SC], 120 [SC], or 240 [SC] mg) or placebo, with safety follow-up. For the first cohort, after the first 2 subjects were dosed (1 active and 1 placebo), there was a minimum gap of 48 hours before the remaining subjects from that cohort were dosed, to allow for an initial review of any emerging safety and tolerability data. For all cohorts, escalation to the next dose was not sooner than 8 days after all the subjects in the prior cohort had been dosed and were based on a review of at least 7 days of safety and tolerability data by the Safety Data Monitoring Team (SDMT).

[figure not shown]
Blood samples were collected at every in-house study visit for BOS161721 concentration determinations. Blood samples were also collected for determination of IL-21 plasma levels (free and total). Safety was assessed based on the occurrence of treatment-emergent AEs, hepatic function abnormality, and acute and delayed hypersensitivity reactions. Other safety variables included electrocardiograms (ECGs), vital signs (blood pressure, heart rate, and temperature), safety laboratory assessments, blood sampling for ADAs, total IgG and IgM levels, CD4+ count, and full and targeted physical examinations. Overall, there were no clinically significant findings from this study, following an interim cut and review of the data at Day 90 postdose. Adverse events reported as related to the study drug, particularly infections, were expected for the compound, and there were no clinically relevant changes in laboratory and ECG results or vital signs. There was 1 serious adverse event (SAE; death due to pulmonary embolism) that occurred 127 days after a single administration of 240 mg SC dose of BOS161721. The causality of this single SAE was not attributed to study drug and further information can be found in the Investigator's Brochure. PK data from the SAD study demonstrates BOS161721 has an extended $t_{1/2}$ (provisional single dose data indicates this to be approximately 42-46 days) which supports evaluation of monthly dosing.

1.2.3 Study Dose Selection

Doses have been selected for the multiple ascending dose (MAD) Phase 1 study based on a 90-day safety, tolerability, PK, and PD data review from the Phase 1 SAD study (BOS161721-01); the SDMT reviewed the blinded safety data from subjects for each dose cohort (8 cohorts, evaluating 1 [IV], 3 [SC], 10 [SC], 22 [IV], 30 [SC], 60 [SC], 120 [SC], or 240 [SC] mg), along with the accumulated safety and available PK/PD data from all subjects in the previous dose cohorts, to make a decision on whether to proceed to the next higher dose level, repeat a dose level, or stop dose escalation. Overall, there were no clinically significant safety or tolerability findings from this study.

Based on the Day-90 interim cut of the PK and biomarker data in the BOS161721-01 study, the recommended doses for evaluation in the MAD phase of this study are 20, 60, and 120 mg SC monthly. This dose recommendation is supported by evidence of linear PK with BOS161721 resulting in a median T_{max} of 6 days and an apparent terminal half-life of 44 days. Furthermore, pSTAT3 suppression, a marker of IL-21 target engagement, follows a similar time course of the mAb levels, with maximal and sustained suppression apparent with doses greater than 30 mg SC (Figure 1).

Figure 1. Individual pSTAT3 C_{min} Levels Versus Dose

IV = intravenous, pSTAT3 = phosphorylated signal transducer and activator of transcription 3; SC = subcutaneous

All doses selected for the MAD study are projected not to exceed the mean exposure of that achieved following the highest single dose of 240 mg SC administered in the Phase 1 SAD study. Cohort 1 will include randomized treatment to the 20 mg dose. Based on the staggered study design, the data monitoring committee (DMC) will perform a scheduled review of safety data and sequentially consider dose escalation for Cohorts 2 and 3. In addition, the DMC and Boston Pharmaceuticals will conduct a data review for the first interim analysis (IA1). At that time, a decision will be made to suggest which dose should be carried forward into the proof of concept (POC) Phase 2 study. This POC dose decision will be based on evaluation of the PK, safety (inclusive of dose-limiting toxicity [DLT]), and tolerability data (and available PD/biomarker data) from Cohorts 1, 2 and 3 from the MAD study (see [Section 4.1.1.1](#)).

1.2.4 Risk-Benefit Assessment

The available preclinical data on BOS161721, the findings in clinical study BOS161721-01, and existing clinical information on IL-21 inhibitors suggest that the present clinical study has an acceptable risk-benefit ratio. In this study, the risk-benefit assessment of BOS161721 in adult patients with moderately to severely active SLE will be ongoing, with step-wise evaluations during the staggered MAD study. The DMC used in this study is charged with assessing such actions in light of an acceptable benefit-risk profile for BOS161721 as an anti-IL-21 mAb. Formal DMC monitoring meetings will occur as described in the DMC Charter. Two weeks after Cohort 1 has received a second dose of study drug, the DMC will evaluate the safety and tolerability data from Cohort 1 to determine the recommended dose for Cohort 2. Two weeks after 8 patients in Cohort 2 receive a second dose, the DMC will determine if dose escalation to Cohort 3 can proceed. Two weeks after the last patient in Cohort 3 receives the second dose, the DMC and Boston Pharmaceuticals will conduct a data review for the IA1. At that time, a decision will be made to suggest which dose should be carried forward into the POC Phase 2 study. This POC dose decision will be based on evaluation of the PK, safety (inclusive of dose-limiting toxicity [DLT]), and tolerability data (and available PD/biomarker data) from Cohorts 1, 2 and 3 during the MAD study. Thereafter, DMC monitoring will be conducted periodically throughout the study as described in the DMC charter. With the agreement of the DMC and sponsor, this schedule may be modified depending on the rate of patient accrual. Additional details can be found in the DMC Charter.

The benefit of participation for all patients in this study is close monitoring of their medical condition and safety of their treatment. Those randomized to the active treatment arm may potentially experience improvement in their SLE disease. Those randomized to the placebo (in combination with standard of care) arm are not expected to obtain any additional benefit, beyond those of their background treatment, though close monitoring of their medical condition and safety may itself be associated with improving their SLE.

1.2.5 Potential Risks

Potential risks based on the mechanism of action of BOS161721 include infections, risks associated with the administration of any foreign protein or biologic agent, including injection site reaction, anaphylaxis, serious allergic reaction, and development of ADAs. ADAs could result in immune complex disease (with manifestations such as arthralgias, serum-sickness, and vasculitis), autoimmunity, or altered BOS161721 levels or activity. Further details can be found

in the current Investigator's Brochure (IB) for BOS161721, which contains comprehensive toxicology, preclinical and clinical information on BOS161721.

Two investigational drug products are considered to be in the same pharmacological class as BOS161721 based on interruption of signaling through the IL-21 signaling pathway. No potential risk generalizable across the class has been observed with these investigational products. Based on the clinical Phase 1 SAD study (BOS161721-01), AEs reported as related to the study drug, particularly infections (flu-like symptoms, etc), were expected for the compound, and there were no clinically relevant changes in laboratory and ECG results or vital signs.

The majority of IgG elimination occurs via intracellular catabolism, following fluid-phase or receptor-mediated endocytosis. This type of endocytosis and elimination is a form of target-mediated disposition where the interaction of the drug and its pharmacological target (eg, a target receptor) serves as a significant contributor to the kinetics of antibody distribution and elimination. Renal elimination, which is a primary pathway of clearance of small-molecule drugs, is relatively unimportant for IgG, as its large size prevents efficient filtration through the glomerulus. Secretion into the bile is an important pathway of elimination of IgA antibodies, but this route is not a significant contributor to the elimination of IgG antibodies. Thus, risk to renal and hepatic systems due to metabolism of BOS161721 is low.³³

1.2.5.1 Anaphylaxis and Serious Allergic Reactions

As with the administration of any foreign protein and/or other biological agents, acute hypersensitivity reactions, including acute anaphylactic/hypersensitivity, severe allergic, and anaphylactoid reactions may follow infusion of mAbs and can be caused by various mechanisms. These acute hypersensitivity reactions may be severe and result in death.

Anaphylaxis will be defined according to the National Institute of Allergy and Infectious Diseases/Food Allergy and Anaphylaxis Network (NIAID/FAAN) criteria,³⁴ and are discussed in [Section 7.2.2.6.1](#).

Based on the limited Phase 1 SAD study (BOS161721-01), anaphylaxis and serious allergic reactions in subjects who received BOS161721 was not observed.

Patients with a known history of allergy or severe hypersensitivity reaction to any component of BOS161721 formulation or patients with a history of anaphylaxis to any other biological therapy such as mAbs will be excluded from studies with BOS161721. In addition, appropriate drugs and medical equipment to treat acute hypotensive, bronchoconstrictive, or anaphylactic reactions will be immediately available at the unit and study personnel will be trained to recognize and treat these reactions.

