 16. Platelets $< 50,000/\text{mm}^3$ ($50 \times 10^9/\text{L}$) or $< 35,000/\text{mm}^3$ ($35 \times 10^9/\text{L}$) if related to SLE, at screening
 17. Hemoglobin $< 8 \text{ g/dL}$ or $< 7 \text{ g/dL}$ at screening if due to anemia related to SLE
 18. Proteinuria $> 3.0 \text{ g/day}$ (3000 mg/day) at screening or equivalent level of proteinuria as assessed by protein/creatinine ratio

(3 mg/mg or 339 mg/mmol)

19. Serum creatinine > 2.0 mg/dL at screening or creatinine clearance (CrCL) < 40 ml/minute based on Cockcroft-Gault calculation
20. Serum alanine aminotransferase (ALT) and/or serum aspartate aminotransferase (AST) > 2 × the upper limit of normal (ULN) at screening, unless explicitly related to lupus based on the investigator's judgment
21. Creatinine kinase (CK) > 3.0 × ULN at screening unless related to lupus myositis
22. Direct bilirubin > 1.5 × ULN at screening (unless related to Gilbert's syndrome)
23. Any other laboratory test results that, in the opinion of the Investigator, might place a patient at unacceptable risk for participating in this study
24. History of allergic or anaphylactic reaction to any therapeutic or diagnostic mAb (eg, IgG protein) or molecules made of components of mAbs
25. History substance and/or alcohol abuse, or dependence within the past 1 year, at the investigator's judgment
26. History of cancer within the last 5 years (except for cutaneous basal cell or squamous cell cancer, or cervical cancer in situ resolved by excision)
27. Any other severe acute or chronic medical or psychiatric condition, including recent (within the past year) medical conditions (eg, cardiovascular conditions, respiratory illnesses) that may increase the risk associated with study participation or investigational product administration or may interfere with the interpretation of study results and, in the judgment of the investigator, would make the patient inappropriate for entry into this study
28. Investigational site staff members directly involved in the conduct of the trial and their family members, site staff members otherwise supervised by the investigator, or patients who are employees of the sponsor or directly involved in the conduct of the trial
29. Currently participating in, or who have participated in other interventional (drug or device) clinical study within 30 days or 5 half-lives of baseline, whichever is longer

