5.5 Exclusion Criteria

Patients presenting with any of the following will not be included in this study:

1. Drug-induced SLE, rather than “idiopathic” SLE
2. Other systemic autoimmune disease (eg, erosive arthritis, rheumatoid arthritis [RA], multiple sclerosis [MS], systemic scleroderma, or vasculitis not related to SLE)
 - a. RA-Lupus overlap (Rupus), and secondary Sjögren syndrome are allowed
3. Any major surgery within 6 weeks of study drug administration, (Day 0), or any elective surgery planned during the course of the study

4. Any history or risk for tuberculosis (TB), specifically those with:
 - a. Current clinical, radiographic, or laboratory evidence of active TB
 - b. History of active TB
 - c. Latent TB defined as positive QuantiFERON-TB Gold In-Tube (QFT-G) or other diagnostic test in the absence of clinical manifestations. Latent TB is not excluded if the patient has documented completion of adequate course of prophylactic treatment with regimen recommended by local health authority guideline, or the patient has started treatment with isoniazid, or other regimen recommended by local health authority guidelines for at least 1 month before Day 0 and continues to receive the prophylactic treatment during study until the treatment course is completed.
5. Active or unstable lupus neuropsychiatric manifestations, including but not limited to any condition defined by BILAG A criteria, with the exception of mononeuritis multiplex and polyneuropathy, which are allowed
6. Severe proliferative lupus nephritis, (WHO Class III, IV), which requires or may require induction treatment with cytotoxic agents or high dose CS
7. Concomitant illness that, in the opinion of the investigator, is likely to require additional systemic glucocorticosteroid therapy during the study, (eg, asthma), is exclusionary
 - a. However, treatment for asthma with inhalational CS therapy is allowed
8. Use or planned use of concomitant medication outside of standard of baseline treatment for SLE from Day -1 or for any time during the study. (See [Section 5.6](#) for prohibited concomitant medication)
9. Active and clinically significant infection (bacterial, fungal, viral, or other) within 60 days prior to first dose of study drug. Clinically significant is defined as requiring systemic antibiotics or hospitalization
10. A history of opportunistic infection, or a history of recurrent or severe disseminated herpes zoster or disseminated herpes simplex within the last 3 years

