11. Chronic viral hepatitis including hepatitis B (HBV) and hepatitis C (HCV), known human immunodeficiency virus (HIV), or acquired immunodeficiency syndrome (AIDS)-related illness
12. Cryptosporidium in the stool sample at screening
13. White blood cells (WBC) $< 1,200/\text{mm}^3$ ($1.2 \times 10^9/\text{L}$) at screening
14. Absolute neutrophil count (ANC) $< 500/\text{mm}^3$ at screening
15. CD4+ count $< 500/\mu\text{L}$ at screening
16. Platelets $< 50,000/\text{mm}^3$ ($50 \times 10^9/\text{L}$) or $< 35,000/\text{mm}^3$ ($35 \times 10^9/\text{L}$) if related to SLE, at screening
17. Hemoglobin < 8 g/dL or < 7 g/dL at screening if due to anemia related to SLE
18. Proteinuria > 3.0 g/day (3000 mg/day) at screening or equivalent level of proteinuria as assessed by protein/creatinine ratio (3 mg/mg or 339 mg/mmol)

19. Serum creatinine > 2.0 mg/dL at screening or creatinine clearance (CrCL) < 40 ml/minute based on Cockcroft-Gault calculation³⁹:

$$\text{GFR} = ([1 \text{ for male}] \text{ or } [0.85 \text{ for female}]) \times (140 - \text{Age}) \times \text{BW} / (72 \times \text{Creatinine})$$

20. Serum ALT and/or serum AST > 2 × ULN at screening, unless explicitly related to lupus based on the investigator's judgment
21. Creatinine kinase (CK) > 3.0 × ULN at screening, unless it is related to lupus myositis
22. Direct bilirubin > 1.5 × ULN at screening (unless related to Gilbert's syndrome)
23. Any other laboratory test results that, in the opinion of the Investigator, might place a patient at unacceptable risk for participating in this study
24. History of allergic or anaphylactic reaction to any therapeutic or diagnostic monoclonal antibody (eg, IgG protein) or molecules made of components of monoclonal antibodies
25. History substance and/or alcohol abuse or dependence within the past 1 year, at the investigator's judgment
26. History of cancer within the last 5 years (except for cutaneous basal cell or squamous cell cancer, or cervical cancer in situ resolved by excision)
27. Any other severe acute or chronic medical or psychiatric condition, including recent (within the past year) medical conditions (eg, cardiovascular conditions, respiratory illnesses) that may increase the risk associated with study participation or investigational product administration or may interfere with the interpretation of study results and, in the judgment of the investigator, would make the patient inappropriate for entry into this study

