5.8 Deviation from Inclusion/Exclusion Criteria

Deviation from the inclusion or exclusion criteria will not be allowed. If deviation of inclusion/exclusion criteria is discovered after randomization, the investigator should contact the medical monitor for discussion. A decision will be made whether to allow a patient continue or withdrawal from the study medication.

See [Section 7.8](#) for additional details.

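### Section 1.2.5.1 (V2.0 and V1.0) excludes two allergy groups that no numbered exclusion criterion names

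*Protocol*

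**What the plan says.** Section 1.2.5.1 of V2.0 deals with anaphylaxis and serious allergic reactions and warns: "These acute hypersensitivity reactions may be severe and result in death". It then commits to two exclusions. The first is "Patients with a known history of allergy or severe hypersensitivity reaction to any component of BOS161721 formulation". The second is patients with a "history of anaphylaxis to any other biological therapy such as mAbs will be excluded from studies with BOS161721". In the second, monoclonal antibodies are given as an example of a biological therapy, not as the limit of the rule.

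The eligibility list in Section 5.5 opens with "Patients presenting with any of the following will not be included in this study" and has 32 numbered items. The one that addresses allergy is criterion 24: "History of allergic or anaphylactic reaction to any therapeutic or diagnostic monoclonal antibody (eg, IgG protein) or molecules made of components of monoclonal antibodies". The V2.0 Protocol Summary repeats it with the same scope: "History of allergic or anaphylactic reaction to any therapeutic or diagnostic mAb (eg, IgG protein) or molecules made of components of mAbs".

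Under Section 6.1, patients are enrolled only after central review confirms them against the lists in Sections 5.4 and 5.5. Section 5.8 adds: "Deviation from the inclusion or exclusion criteria will not be allowed".

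V1.0 has the same text in Section 1.2.5.1 and the same scope in criterion 24.

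**The concern.** The risk section and the operative list disagree on who is excluded. Anyone applying the list as written finds no specific item that stops a patient with a known allergy to an excipient, or one who has had anaphylaxis to a biologic that is neither an antibody nor made from antibody components. A firm commitment in Section 1.2.5.1 becomes a judgment call at screening, and sites may judge differently.

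What is at stake is patient safety, not inference. The protocol itself describes these reactions as potentially fatal. V3.0 Section 6.2.2.6 puts anaphylaxis and serious allergic reactions first among the adverse events of special interest, and each patient may receive up to seven injections. The emergency equipment and trained staff in Section 1.2.5.1, and the mandatory discontinuation in V3.0 Section 6.2.2.6.1, act only once a reaction has begun. Exclusion at entry is the preventive step, and the sponsor has already chosen it.

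**Working it through.** No arithmetic beyond a count applies. The check sets the two texts side by side and then looks for any other item that closes the gap.

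**Scope of each text (V2.0)**

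| Patient history | Section 1.2.5.1 | Criterion 24 |
|---|---|---|
| Anaphylaxis to a monoclonal antibody or antibody-derived molecule | Excluded | Excluded |
| Milder allergic reaction to the same | Not mentioned, unless it concerns a component of the study drug | Excluded |
| Allergy or severe hypersensitivity to a formulation component that is not antibody-based | Excluded | Not named |
| Anaphylaxis to a biologic that is neither an antibody nor antibody-derived | Excluded | Not named |

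For antibodies, criterion 24 is the stricter text, since any allergic reaction excludes. The gap is confined to the last two rows.

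**Count over the numbered exclusions in Section 5.5**

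- Numbered exclusions: 32
- Naming allergy to a formulation component: 0
- Naming anaphylaxis to a biologic that is not antibody-based: 0
- Naming allergy to monoclonal antibodies: 1 (criterion 24)
- General item that could catch either group by judgment: 1 (criterion 27)

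The same count holds in V1.0: 32, 0, 0, 1, 1.

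**Other items that might close the gap**

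- Criterion 27 requires a severe medical or psychiatric condition that, "in the judgment of the investigator, would make the patient inappropriate for entry into this study". A past excipient allergy does not obviously qualify, and the decision is discretionary.
- Section 5.6.2 lists prior exposure to the study drug as prohibited. That does not cover an excipient the patient met in another product.
- Section 5.3 asks that all relevant conditions be weighed, with the medical monitor or a designee confirming eligibility before randomization. V3.0 Section 10 likewise has the medical monitor determine eligibility. Either can keep such a patient out, but neither names either group.

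**Status of the wording**

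V2.0 is superseded, and V3.0 Section 1.2.5.1 and its exclusion list are not in the text available here. The V3.0 summary of changes (Appendix 7) runs in section order. At the relevant places it goes from Section 1.2.4 to Section 2 and from Section 4.4 to Section 5.1, with no entry for Section 1.2.5.1 or for the exclusion criteria. It does record an edit as slight as a change of verb tense in inclusion criterion 6. This points to carry-over but does not prove it.

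**The case against.** The strongest objection is that neither half of the contradiction is shown in the current version. Appendix 7 claims to list only significant changes, and it is visibly incomplete: V2.0 Section 7.6 lists whole blood RNA among the pharmacodynamic parameters, V3.0 Section 6.6 does not, and no visible entry for that section records the deletion. Silence in the log therefore cannot establish that the wording survives. This stands, and it is why the conclusion is limited to V2.0 and V1.0 and the first step is to confirm the current text.

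A second objection reads Section 1.2.5.1 as background on the whole programme, because it speaks of studies with the drug in the plural. This does not stand. Section 1.2.5.4 uses the same phrase for patients with a history of opportunistic infection, and this trial carries that exclusion into its list as criterion 10.

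A third objection is that the two groups may be very small or empty. The formulation is redacted, so nobody can say from the document whether it contains a plausible allergen. Several products in Appendix 4 that are not monoclonal antibodies are immunoglobulins or immunoglobulin constructs, and they arguably fall under criterion 24 already. Section 5.6 foresees prior biologic treatment for lupus but does not say how often it would be a biologic outside that class. This limits the size of the point but does not remove the mismatch: both sentences are fully legible and they differ.

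Finally, the medical monitor, criterion 27 and the medical history taken at screening give some cover. That is true, but the cover is discretionary where Section 1.2.5.1 is categorical.

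**Conclusion.** The inconsistency is real in V2.0 and V1.0. Two groups that Section 1.2.5.1 says will be excluded appear in 0 of the 32 numbered exclusions, and 1 of the 32 could catch them by judgment. Central review against the list could therefore admit a patient whom the protocol says it excludes.

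The point is minor. The number of patients affected cannot be derived, because the formulation is redacted and no allergy frequencies are given. Criterion 24 is already stricter than the risk text for antibodies, and emergency and discontinuation provisions remain. Sample size, power, type I error and the primary analysis are not affected. Relevance to the current protocol assumes that the V3.0 wording of both sections is unchanged, which is likely but unconfirmed.

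**What to change.** First check whether the current version still has both texts. If it does, keep the existing monoclonal antibody wording of criterion 24, including its coverage of any allergic reaction. Add a clause excluding known allergy or severe hypersensitivity to any ingredient of the study drug formulation, and anaphylaxis to any biological product. Make the same addition in the Protocol Summary copy of criterion 24 and in the eligibility checklist.

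The cost is one line in each of those three places at the next amendment, and possibly a few more screen failures.
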